#### **4.1 Overall Research Design:**

This research plan proposes experiments that are critical to advance our understanding of glutamatergic signaling in alcohol use disorders. We will recruit moderate drinkers and Alcohol Use Disorder subjects between the ages of 21 to 55 years to participate in the recruitment, evaluation, and imaging. Moderate drinkers are defined as people who report consuming alcohol on at least one occasion in the past three months that would result in an estimated blood alcohol level greater than 80 mg/dl but not meet DSM-5 criteria for AUD. This is operationally defined as more than 3 standard drinks in a single occasion for women and 4 standard drinks in a single occasion for men. All participating subjects will be seen for an initial intake, including a full physical exam and medical coding. Thereafter, they will have an anatomical MRI scan, followed by a series of [C]ABP688 and/or [F]FPEB PET scans with alcohol challenge as described in the below aims:

**Aim 1** will evaluate the sensitivity of the mGlu5 radioligand [F]FPEB to alcohol release in the same subjects (moderate drinkers,  $n=10$ ). Subjects will participate in up to two [F]FPEB scans with alcohol challenge that measure mGlu5 availability under the following conditions: baseline and 60 mg/dL alcohol administration. This will be conducted with the following sub-aims:

**Aim 1a** will administer the alcohol (targeting 60 mg/dL) as an oral challenge. This will be done in at least the first 5 subjects. At this point, the percent change in mGlu5 receptor availability (i.e., [F]FPEB  $V_T$ ) will be evaluated. If this remains within test-retest estimates of this radiotracer (9-12%) {Park, 2015 #219} in subjects achieving the targeted alcohol dose, then we may proceed to Aim 1b:

**Aim 1b** will administer the alcohol (targeting 60 mg/dL) as an i.v. challenge.

**Aim 2** will evaluate the sensitivity of the mGlu5 radioligand [C]ABP688 to alcohol release in the same subjects (moderate drinkers,  $n=10$ ). Subjects will participate in up to two [C]ABP688 scans with alcohol challenge that measure mGlu5 availability under the following conditions: baseline and 60 mg/dL alcohol administration. This will be conducted with the following sub-aims:

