**Aim 2a** will administer the alcohol (targeting 60 mg/dL) as an oral challenge. This will be done in at least the first 5 subjects. At this point, the percent change in mGlu5 receptor availability (i.e., [C]ABP688  $V_T$ ) will be evaluated. If this remain within test-retest estimates of this radiotracer (<12%) in subjects achieving the targeted alcohol dose, then we may proceed to Aim 2b:

**Aim 2b** will administer the alcohol (targeting 60 mg/dL) as an i.v. challenge.

We will strive to recruit the same subjects from Aim 1 for Aim 2, in order to directly compare the two experimental approaches in the same people.

The results of these two aims will inform the selection of an optimal experimental design.

**Aim 3** will compare the alcohol-induced glutamate release in moderate drinkers ( $n=30$ , including subjects from the chosen tracer from Aim 1 or 2) and individuals with alcohol use disorder ( $n=30$ ). Subjects will participate in up to two mGlu5 scans under the following conditions: baseline and 60 mg/dl alcohol administration.

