#### Breakdown of Aims 1-3

- Aim 1: 10 moderate drinkers
- Aim 2: 10 moderate drinkers

- Aim 3: 30 moderate drinkers (minus drinkers from chosen tracer in Aim 1 or 2), and 30 AUD

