#### Laboratory Alcohol Session

Laboratory sessions will occur at the Yale PET Center. Subject body weight will be acquired during intake as part of the medical history and used for alcohol dose calculations. Subjects will be asked not to diet between intake and study days. Alcohol dose will be recalculated if the subject's weight varies by more than 5 pounds for women and 10 pounds for men. Confirmation of alcohol abstinence will be made via self-report and breathalyzer on study day. Subjects will be given a light standardized breakfast on arrival to the laboratory and the morning prior to discharge.

Prior to alcohol administration, subjects will have a standardized light lunch to increase tolerability of the alcohol dose while minimizing the potential for variations in food intake that could affect alcohol metabolism.

Oral alcohol challenge: Alcohol will be administered in the form of 80 proof vodka and a mixer based on the subject's choice of water or a decarbonated noncaffeinated noncaloric soda. The dose will be prepared by the research team and take into account the participant's total body water (based on gender, age, height, and weight), duration of drinking, and ratio of alcohol to mixer, based on Watson et al's update of the Widmark equation. The total volume will be divided into three equal drinks, with each consumed over a 10-minute period to control the rate of consumption. This pacing aims to reduce risk of nausea. After the session subjects may drink water ad lib until scanning. Subjects will be asked to void prior to the second PET scan. Afterwards, subjects will be given dinner based on food preferences. Water, crackers, and other snacks will be available ad lib for the rest of the evening.

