#### Assessments following alcohol administration:

BrAC will be measured at 15 min intervals beginning at alcohol administration and continuing until the end of scanning procedures. Vital signs will be measured concurrently. Should the measured BAC reach or exceed the targeted 60dose, then subjects will end further alcohol drinking. Other assessments that may be collected during these times include inflammation markers, self-reports of alcohol effects and mood.

1. Blood Alcohol Concentrations: Blood samples will be collected in gray stoppered (oxalate, fluoride) tubes and analyzed with gas chromatography analyses in the Yale-New Haven Hospital Clinical Laboratories. After microfuging, serum will be transferred into microtubes and stored at -20°C until assay.
2. Breath Alcohol Concentrations will be determined with an Alcohol-Sensor III (Intoximeter Inc., St. Louis, MO).
3. Inflammation Markers: Serum levels of cytokines, such as TNF- $\alpha$ , IL-1 $\beta$ , IL-4, IL-6, and IL-8, and cortisol will be measured at baseline and when blood is drawn to measure BAL. We may also collect monocytes to assess immune function *in vitro*.
4. Visual Analog Scale (VAS) self-ratings for drug effects. Subjects will answer questions to assess behavioral changes induced by substance use.
5. Subjective Effects of Alcohol Scale is a self-report measure that assesses subjective experience of alcohol effects following alcohol administration.
6. Biphasic Alcohol Effects Scale is a self-report questionnaire that assesses subjective experiences of alcohol stimulation and sedation.
7. Self-Rating the Effects of Alcohol (SRE) is a retrospective self-report questionnaire measuring the response to alcohol.
8. Columbia Suicide Severity Rating Scale (CSSRS) is a clinician administered questionnaire to assess suicidality. In the event of an unexpected outcome, subjects will be referred to the Emergency Department for risk assessment.

The total amount of blood drawn during the study will not exceed 32 tablespoons total.

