#### **Risks Associated with Oral Alcohol**

Alcohol may induce nausea in high doses; however, significant nausea is not expected at the targeted dose for this study because subjects will have consumed a light lunch and they will have had recent (in the last three months) experience with the targeted alcohol dose. Other side effects resulting from oral alcohol may include blurred vision, nausea, vomiting, flushing, headache, and lightheadedness. Subjects will be permitted to decline further drinking if they so choose.

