**AIM 3:** The primary outcome measure will be the alcohol-induced change in mGlu5 availability, estimated as  $\Delta V_T = (V_T(\text{Alcohol}) - V_T(\text{Baseline})) / V_T(\text{Baseline})$ . The value of  $\Delta V_T$  will then be used as the primary outcome measurement for subsequent analyses.

To test the hypotheses that glutamate responses to alcohol are lower in heavy drinkers compared to moderate drinkers, a linear mixed model featuring group (heavy alcohol use vs. moderate use) as a between-subject fixed factor and region as a within subjects factor will be constructed. The main effect of group will be examined to test the null hypothesis of no difference in  $\Delta V_T$  between study groups. The interaction term between the two factors will also be examined. Post-hoc linear contrasts will examine regional differences in radiotracer  $\Delta V_T$  between groups.

Exploratory analyses at the voxel level will be conducted for all aims using whole brain data and SPM12.

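### Aim 3 compares the groups' change in V_T without using the alcohol exposure actually achieved, so unequal exposure in either direction could mimic or hide blunted glutamate release

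*Combined protocol and SAP*

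**What the plan says.** Aim 3 compares "30 moderate drinkers (minus drinkers from chosen tracer in Aim 1 or 2), and 30 AUD". The outcome is the proportional change in V_T from baseline to the alcohol scan. Item 13 sets out a linear mixed model with "group (heavy alcohol use vs. moderate use) as a between-subject fixed factor and region as a within subjects factor will be constructed", plus the interaction of the two. "The main effect of group will be examined to test the null hypothesis of no difference in" ΔV_T between the groups. No term, restriction or sensitivity analysis refers to the alcohol level reached. The Aim 3 paragraph of section 4.1 names the 60 mg/dL condition as a target only.

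Achieved exposure does appear in section 4.1, in the decision whether to move from oral to i.v. alcohol. There the V_T change is judged "in subjects achieving the targeted alcohol dose, then we may proceed to Aim 1b", and for the second tracer "in subjects achieving the targeted alcohol dose, then we may proceed to Aim 2b".

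On delivery:

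- **Oral** (Laboratory Alcohol Session): the dose is calculated from "total body water (based on gender, age, height, and weight), duration of drinking, and ratio of alcohol to mixer".
- **I.v.** (same section): an infusion profile is worked out in advance from height and weight to hold 60 mg/dL. No adjustment to measured levels is described.
- **Stopping at target** (Assessments following alcohol administration): "Should the measured BAC reach or exceed the targeted 60dose, then subjects will end further alcohol drinking". Nothing is said about subjects who stay below target.
- **Declining** (Risks Associated with Oral Alcohol): "Subjects will be permitted to decline further drinking if they so choose". The section on infused alcohol gives the same option.

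On measurement, breath alcohol is read every 15 minutes from the start of administration to the end of scanning. Blood alcohol is sampled as well (PET Data Acquisition and Analysis; Assessments following alcohol administration).

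**The concern.** The Statement of Purpose would read a smaller ΔV_T in AUD as evidence of neuroadaptation in glutamate signalling. That reading needs the two groups to have met a comparable alcohol challenge, and the plan neither secures this nor checks it. If AUD subjects had less alcohol on board during the scan, their ΔV_T could be smaller with no difference in glutamate signalling. If they had more, real blunting could be masked. The Aim 3 model cannot tell these cases apart, although the readings needed to examine them are already being taken. The route decision shows that the investigators regard achieved exposure as relevant to interpreting ΔV_T.

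**Working it through.** **1. No planned figure to reproduce.** The documents state no power, alpha, SD or expected effect for the 30 versus 30 comparison. What follows is a sensitivity calculation.

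**2. Inputs.**

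- From the documents: n = 30 per group; target 60 mg/dL. The only variability figure is a test-retest variability below 12%.
- Assumed: two-sided alpha 0.05; one ΔV_T value per subject (averaged over regions) with SD 8, 10 or 12 points; a V_T fall of E = 10% at 60 mg/dL; response proportional to alcohol level; no true group difference in response per unit of alcohol; exposure in AUD short by a fraction s of 10% or 20% (54 or 48 mg/dL instead of 60).

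**3. Formulas.**

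- Spurious group difference: D = E × s, so 10 × 0.10 = 1.0 point or 10 × 0.20 = 2.0 points.
- SE = SD × √(2/30), so 2.07, 2.58 or 3.10 points for SD 8, 10 or 12.
- Chance of a significant group effect = Φ(D/SE − 1.96) + Φ(−D/SE − 1.96).

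Example (s = 20%, SD 8): D/SE = 2.0/2.07 = 0.97, giving Φ(−0.99) + Φ(−2.93) ≈ 0.160 + 0.002 = 0.162.

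| Exposure in AUD | D | SD 8 | SD 10 | SD 12 |
|---|---|---|---|---|
| 54 mg/dL (10% short) | 1.0 | 7.7% | 6.7% | 6.2% |
| 48 mg/dL (20% short) | 2.0 | 16.2% | 12.1% | 9.9% |

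The nominal rate is 5%. Larger assumed inputs give larger rates: with a 15% effect and a 30% shortfall the range is 30.6 to 58.7%. Nothing in the documents supports one setting over another.

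**4. Scale.** The difference detectable with 80% power is (1.96 + 0.84) × SE, about 0.72 SD: 5.8, 7.2 or 8.7 points for SD 8, 10 or 12. A spurious 1 to 2 points is therefore about 12% (1.0/8.7) to 34% (2.0/5.8) of it.

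**5. Opposite direction.** Suppose moderate drinkers average 48 mg/dL and AUD subjects 60, and the true AUD response at 60 is 8% rather than 10%. Moderate drinkers then show 10 × 48/60 = 8%, AUD subjects also show 8%, and a real 2-point blunting disappears.

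**6. Does adjustment help?** Simulation used 3,000 runs per setting and a between-subject SD of alcohol level of 10 mg/dL (assumed). With a 10% effect, 20% shortfall and SD 10, the group-only model rejected in 11.0% of runs; adding achieved alcohol level brought this to 4.6%. Over four settings the adjusted rate was 4.2 to 5.1%, and the mean adjusted group difference was within 0.1 point of zero. The simulation builds in a linear response and exposure measured without error.

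**The case against.** **The direction is not in the documents.** A reader might infer that AUD subjects will have lower alcohol levels, for instance by faster clearance, and that the bias therefore favours the hypothesis. No section gives elimination rates or says that levels will differ by group. Early stopping by moderate drinkers would push the other way. This objection stands.

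**Nothing was removed from the analysis.** A reader might infer that Aim 3 abandons an analysis condition used in Aims 1 and 2. The achieved-target wording belongs to the oral-to-i.v. decision. The Aims 1 and 2 mixed model has no such condition either, and the wording gives no tolerance, time point or measure that Aim 3 could reuse. This also stands.

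**Delivery is partly controlled.** Dosing by body water, a standardised lunch, paced drinks, the stop at target and an infusion designed to hold 60 mg/dL should all narrow differences. They do not equalise exposure. Scanning is described as starting after the challenge is completed, by up to 30 minutes, with acquisition of up to 120 or 180 minutes depending on tracer, so levels can move apart during the scan by either route.

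**The response may follow the peak, or may not be linear.** The plan times the scan to the peak glutamate response. If V_T tracks the peak alone, mean exposure over the scan is the wrong summary, and a linear term could misfit. This limits how much weight the adjusted model can carry.

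**Adjustment changes the question.** It moves from response to the challenge as given towards response at equal exposure. That is closer to the stated hypothesis about glutamate signalling, but if exposure depends strongly on group, adjustment becomes extrapolation. Hence the unadjusted test should stay, with the adjusted model supportive.

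**Conclusion.** The concern holds as a gap in the analysis plan. Aim 3 tests the group effect with no use of achieved alcohol exposure, delivery is not equalised, and the relevant readings are already collected. As written, a group difference, or its absence, cannot be separated from unequal exposure.

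The size is unknown. Under the assumptions in the working (10% V_T effect, SD 8 to 12 points, proportional response), a 10 to 20% shortfall in AUD gives a false-positive rate of about 6 to 16% instead of 5%; at the low end this is minor. An imbalance the other way would hide a true effect. The documents do not support a claim that Aim 3 is biased towards its hypothesis, only that it could be biased either way without anyone being able to see it.

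**What to change.** Before Aim 3 data are seen, add to item 13:

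1. **A derived exposure variable:** mean breath alcohol (or plasma alcohol) over the acquisition of each alcohol scan, summarised by group.
2. **The present group test, kept unadjusted.**
3. **A supportive model** that adds this exposure to group, region and their interaction.
4. **A sensitivity analysis** in subjects within an achieved-exposure range, with its measure, time window and tolerance written down in advance, since section 4.1 defines none.
5. **Interpretation:** discuss a group difference as altered glutamate signalling in light of whether it is consistent at comparable exposure. Show the overlap of exposure between groups, and state that adjustment relies on that overlap and on a roughly linear response. This should guide interpretation, not act as a pass/fail rule, given 30 subjects per group.

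The cost is protocol wording, one variable from readings already planned, and one degree of freedom in the supportive model. The sensitivity analysis will lose some subjects and precision. No procedure or alcohol administration changes.

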## SECTION II: RESEARCH INVOLVING DRUGS, BIOLOGICS, RADIOTRACERS, PLACEBOS AND DEVICES

*If this section (or one of its parts, A or B) is not applicable, check off N/A and delete the rest of the section.*

### A. RADIOTRACERS

N/A

1. Name of the radiotracer: **[C]ABP688 and [F]FPEB** (radiotracer for PET studies), IV
2. Is the radiotracer FDA approved?  YES  NO

If NO, an FDA issued IND is required for the investigational use unless RDRC assumes oversight.

3. Check one:  IND# or  RDRC oversight (RDRC approval will be required prior to use)
4. **Background Information:** Provide a description of previous human use, known risks, and data addressing dosage(s), interval(s), route(s) of administration, and any other factors that might influence risks. If this is the first time this radiotracer is being administered to humans, include relevant data on animal models.

#### [C]ABP688

The radiotracer [C]ABP688 has been used in human subjects previously, including at Yale University. Over 170 injections and more than 80 individuals have been given this radiotracer at Yale. No subjects have reported any adverse event with this radiotracer. However, subjects will be monitored carefully during and after the PET scan for any potential side effects.

[C]ABP688 is administered intravenously at doses up to 20 mCi per single injection which is below the 21 CFR 361.1 estimated permissible single administration dose limit of 82 mCi based on dosimetry calculations.

#### [F]FPEB

The radiotracer [F]FPEB has previously been used in human subjects, including Yale University. Over 200 individuals and over 352 injections have been imaged at Yale University. No subjects have reported any adverse event with this radiotracer. However, subjects will be monitored carefully during and after the PET scan for any potential side effects.

[F]FPEB is administered intravenously at doses up to 5 mCi per single administration which is below the 21 CFR 361.1 estimated permissible single administration dose limit of 7 mCi based on dosimetry calculations with 3.5 h voiding period.

4. **Source:** Identify the source of the radiotracer to be used.

[C]ABP688 and [F]FPEB will be synthesized at the Yale University PET Center radiochemistry Laboratory under the supervision of [name] and [name].

5. **Storage, Preparation and Use:** Describe the method of storage, preparation, stability information, method of sterilization and method of testing sterility and pyrogenicity.

[C]ABP688 and [F]FPEB will be prepared at the Yale PET Center in accordance with procedures and quality specifications described in local Drug Master File (DMF) approved by the Yale University Radioactive Drug Research Committee (YURDRC) and the Yale University Radiation Safety Committee (YURSC).

Due to the short half-life, PET drugs are produced *ex tempore* and formulated immediately before administration, and therefore there are no issues with storage or stability. PET drug products are stored at room temperature and are stable for at least 60 minutes after preparation.

The preparation of sterile and pyrogen free PET drug products is validated prior to human use. Sterility is achieved by passing the PET drug products through a 0.22 micron membrane filter during the last step of the formulation process. Due to the short half-life, a sample of the PET drug product is tested for sterility *ex post facto* for further confirmation. However and prior to release for administration, a bubble point test is performed on the membrane filter used for terminal sterilization in order to validate and verify its integrity during the filtration process. Also prior to release of the final PET drug product for administration, the level of endotoxin in each batch is determined quantitatively using the FDA approved Charles River Laboratory's Portable Testing System (Endosafe®-PTS).

B. DRUGS/BIOLOGICS  **N/A**

1. If an **exemption from IND filing requirements** is sought for a clinical investigation of a drug product that is lawfully marketed in the United States, review the following categories and complete the category that applies (*and delete the inapplicable categories*):

Exempt Category 1: The clinical investigation of a drug product that is lawfully marketed in the United States can be exempt from IND regulations if all of the following are yes:	
1. The intention of the investigation is NOT to report to the FDA as a well-controlled study in support of a new indication for use or to be used to support any other significant change in the labeling for the drug.	
2. The drug that is undergoing investigation is lawfully marketed as a prescription drug product, and the intention of the investigation is NOT to support a significant change in the advertising for the product.	
3. The investigation does NOT involve a route of administration or dosage level or use in populations or other factor that significantly increases the risks (or decreases the acceptability of the risks) associated with the use of the drug product	

4. The investigation will be conducted in compliance with the requirements for institutional (HIC) review and with the requirements for informed consent of the FDA regulations (21 CFR Part 50 and 21 CFR Part 56).	
5. The investigation will be conducted in compliance with the requirements regarding promotion and charging for investigational drugs.	

**Exempt Category 2** (all items i, ii, and iii must be checked to grant a category 2 exemption)

- i. The clinical investigation is for an *in vitro* diagnostic biological product that involves one or more of the following (check all that apply):
  - Blood grouping serum
  - Reagent red blood cells
  - Anti-human globulin
- ii. The diagnostic test is intended to be used in a diagnostic procedure that confirms the diagnosis made by another, medically established, diagnostic product or procedure; and
- iii. The diagnostic test is shipped in compliance with 21 CFR §312.160.

